3.1.2.6. Visit 6 (EOT for Cohorts 1-3) (Week 12 ±3 days)

Visit 6 will be conducted as an outpatient visit. The following activities will be performed:

- Review concomitant medications for any changes
- Pregnancy test for FOCP (urine)
- Safety labs (see [Appendix 1](#))
- Pharmacodynamics (ACTH, 17-OHP, A4, testosterone, and 11KT) drawn prior to GC dosing at approximately 8 AM (±1 hour). Fasting is not required.
- Cortisol
- Tildacerfont concentration (single sample) drawn prior to GC dosing at approximately 8 AM (±1 hour). Fasting is not required.
- GC dosing adjustments (for Cohort 1-3 patients who are continuing in the EP) to be determined after A4 value is resulted
- Urinalysis
- Vital signs: blood pressure, pulse rate, body temperature, respiration rate, and weight
- Physical exam (full)

- 12-lead ECG
- Suicidality Questionnaire- C-SSRS since last visit (participants aged 6- to 17-years only)
- Depression and Anxiety Questionnaires (PROMIS or SWYC depending on age of participant)
- Study drug accountability
- Assess for AEs

3.1.2.7. Safety Follow-up Visit Telephone Call (30 days after last dose \pm 7 days)

Approximately 30 days after the last dose of study drug (post the 12- or 4-week treatment period, depending on cohort, or post the extension), participants will have a final follow-up visit conducted by telephone. Concomitant medications and AEs will be reviewed. If any ongoing safety issues are identified, the participant may be asked to visit the clinic for additional tests, labs, or assessments.

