#### 9.4.14 Responder Definitions

The second secondary efficacy and exploratory variables are proportions of responders based on serum PD assessments and GC dosing. Indicator variables for each responder criteria are defined in [Table 5](#).

**Table 5** Responder Definition by Endpoint

Endpoint	Definition	
Composite: Proportion of subjects who achieve reduction in A4 OR reduction in GC dosing (Cohorts 1 through 3) at a postbaseline visit	1	Reduction in A4 OR reduction in GC Dose
	0	(no reduction in A4 AND no reduction in GC Dose) OR missing
Proportion of subjects with elevated baseline A4 who achieve a reduction in A4 at a post-baseline visit	1	Baseline A4 > ULN AND reduction in A4
	0	Baseline A4 ≤ ULN OR no reduction in A4 OR missing
Any reduction at a postbaseline visit	1	Reduction from baseline
	0	No reduction from baseline OR missing
≥ 50% reduction at a postbaseline visit	1	≥ 50% reduction from baseline
	0	< 50% reduction from baseline OR missing
≤ ULN at a post-baseline visit	1	≤ ULN
	0	> ULN OR missing

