#### *9.4.17.3 Glucocorticoid Dose at Visit*

Based on the GC therapies collected in the A4-based GC Dose Adjustment eCRF form, GC dose at visit is collected under the question, “Total GC Dose (mg)”.

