## **12.3 Glucocorticoid Regimen**

Concomitant GC therapy will be summarized for each cohort of the study. The source of GC dosing is the A4-based GC Dose Adjustment eCRF.

Descriptive statistics for GC dose (in mg HCe) and BSA-adjusted GC dose will be summarized by cohort and scheduled time point. In addition, the number and percentage of subjects who

decrease their dose of GC regimen will be summarized by cohort. All the above information will be included in a subject listing.

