### 13.1 Secondary Efficacy Analysis

The secondary “treatment policy” estimands are evaluated by two secondary efficacy assessments.

#### 13.1.1 Reduction in A4 or Reduction in GC Dosing at Week 12

Population: The analysis population for the secondary efficacy analyses is the PD analysis set.

Variable: The analysis variable is the proportion of subjects in the PD analysis set who are responders (defined in [Table 5](#)). This proportion is calculated for each cohort as the number of subjects at Week 12 (at Week 4 for cohorts 4 through 9) who have a reduction of A4 or reduction in GC reduction, divided by the total number of subjects in the PD analysis who were enrolled in each cohort. This proportion is also calculated to evaluate the overall subjects at Week 12 (at Week 4 for cohorts 4 through 9) by pooling the responders and dividing by the total number of subjects in the PD analysis set.

Subjects with missing A4 or GC dosing information at a given visit are assumed to be non-responders at that visit. Subjects who do not have a reduction from baseline in A4 or a reduction in GC dose are considered non-responders.

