 In all cohorts, GC dose (frequency or total daily dose) may be adjusted based on A4 levels collected at Weeks 4 and 8 (all participants) and Week 12 (for those participants continuing in the optional EP). If a change in GC is warranted by the A4 algorithm, sites will contact participants by telephone after receipt of results (within approximately 2 weeks) after each applicable study visit.

 Urinalysis should include the following: specific gravity, pH, glucose, protein, blood, ketones, bilirubin, urobilinogen, nitrite, by dipstick. Microscopic examination should be obtained if blood or protein is abnormal. For visits in which tildacerfont is administered, urinalysis should be performed pre-dose.

 Systolic and diastolic blood pressure, pulse rate, body temperature, and respiration rate. Height will only be collected every 6 months.

 Full physical exam is performed at Visit 2, Visit 6, and ET Visit; an abbreviated/directed physical exam is performed at all other visits.

 Day 1 ECGs are conducted pre-dose. Day 14 ECG is dose independent, as participants should be at steady state.

 Historical bone age and predicted adult height calculation may be used if performed  $\leq$ 6 months prior to Screening. If no appropriate image is available, x-ray of left hand and wrist will be performed to assess bone age and calculate predicted adult height.

 The C-SSRS, to assess suicidality, is only conducted for participants aged 6 to 17 years.

 PROMIS, to assess anxiety and depression, is conducted for participants aged 5 to 17 years.

 The SWYC to assess anxiety and depression is only conducted in Cohort 3 participants  $\leq$ 5 years of age.

 A 12-week supply of study drug will be dispensed at Visit 2 (Day 1). Participants should bring study drug to all visits for accountability. Upon receipt of study drug, the pharmacy will hold/store two doses to ensure that in-clinic dosing can occur at Visit 3 (Week 2) in the event a participant does not bring study drug to the visit.

 Cohorts 1 and 2 dosing:

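### SAP 13.1.1, read literally, scores an observed reduction as non-response when the other half of the A4-or-GC composite is missing

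*SAP*

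**What the plan says.** **The rule.** SAP 13.1.1 takes its responder definition from Table 5 and then states: "Subjects with missing A4 or GC dosing information at a given visit are assumed to be non-responders at that visit".

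**Table 5 (SAP 9.4.14).** For the composite, code 1 is "Reduction in A4 OR reduction in GC Dose". Code 0 is "no reduction in A4 AND no reduction in GC Dose) OR missing". The last word is not qualified: it could mean one component missing or both.

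**Source of GC dose.** SAP 12.3: "The source of GC dosing is the A4-based GC Dose Adjustment eCRF". SAP 9.4.17.3 agrees: "Based on the GC therapies collected in the A4-based GC Dose Adjustment eCRF form, GC dose at visit is collected under the question" on total GC dose in mg.

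**When GC is adjusted.** At Week 12, Protocol 3.1.2.6 lists "GC dosing adjustments (for Cohort 1-3 patients who are continuing in the EP". SAP Table 8, footnote 10, allows adjustment at Weeks 4 and 8 for everyone in Cohorts 1-3, "and Week 12 (for those participants continuing in the optional EP". SAP Table 10, footnote 10, puts the same limit on Week 4 in Cohorts 4-9. The schedule rows themselves carry an X at these visits. Neither document says when the eCRF page has to be completed.

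**Denominator.** The PD analysis set (SAP Section 8) requires a post-baseline A4 but no post-baseline GC dose.

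**Cohorts 4-9.** SAP 6.1.2 gives these cohorts A4 endpoints only, and Table 5 labels the composite as belonging to Cohorts 1 through 3. SAP Table 3 nevertheless sends their endpoint to 13.1.1, which applies the A4-or-GC rule to them at Week 4.

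**The concern.** In an either/or composite, one observed success settles the outcome, and the missing component cannot change it. Treating missing data as failure is a normal conservative convention when the outcome is unknown. Here the literal sentence also applies it where the outcome is known. It discards an observed response and keeps the subject in the denominator, so the error runs in one direction only.

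Cohorts of 5 or 10 make each such subject visible in the reported percentage. The SAP also leaves the programmer a choice: Table 5 code 1 points one way, the 13.1.1 sentence points the other, and the end of code 0 can be read either way. Two competent programmers could report different rates from the same data.

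**Working it through.** **Inputs.** The plan gives no responder rate, power or calculated sample size for this endpoint, so there is no figure of its own to reproduce. The planned cohort sizes in SAP Table 1, used here as denominators, do add up: 5+5+5+10+5+10+5+10+5+10 = 70. Cohorts 1-3 with optional Cohort 1a give 5+5+5+10 = 25. The interval method is exact Clopper-Pearson (SAP 13.1.1.1.1).

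**Step 1: compare the scorings.** Each component can be reduced, not reduced or missing, which gives nine states.

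| A4 | GC dose | 13.1.1 read literally | Either observed reduction counts |
|---|---|---|---|
| reduced | reduced | 1 | 1 |
| reduced | not reduced | 1 | 1 |
| reduced | missing | **0** | **1** |
| not reduced | reduced | 1 | 1 |
| not reduced | not reduced | 0 | 0 |
| not reduced | missing | 0 | 0 |
| missing | reduced | **0** | **1** |
| missing | not reduced | 0 | 0 |
| missing | missing | 0 | 0 |

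The scorings differ in two states. In both, code 1 is already met by what was observed, so the literal reading can only lower the rate.

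**Step 2: effect per subject.** Each affected subject moves the rate by 1/n: 1/5 = 20 points, 1/10 = 10 points, 1/25 = 4 points.

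**Step 3: illustration.** Assume a true response rate of 80%.

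| n | No responder affected | Some affected | Literal rate |
|---|---|---|---|
| 5 | 4/5 = 80.0% (28.4-99.5) | 1 | 3/5 = 60.0% (14.7-94.7) |
| 5 | as above | 2 | 2/5 = 40.0% (5.3-85.3) |
| 10 | 8/10 = 80.0% (44.4-97.5) | 2 | 6/10 = 60.0% (26.2-87.8) |
| 25 | 20/25 = 80.0% (59.3-93.2) | 5 | 15/25 = 60.0% (38.7-78.9) |

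**Step 4: range.** Let p be the true composite rate and m the share of responders whose other component is missing. The expected literal rate is p(1-m), a shift of -pm. Neither p nor m is in the documents, so both are assumed.

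- p = 0.5: 0 at m = 0, -5 points at m = 10%, -25 points at m = 50%.
- p = 0.7: 0, -7 and -35 points.
- p = 0.9: 0, -9 and -45 points.

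**Step 5: Cohorts 4-9.** SAP 9.4.17.4 sets the Day 1 GC dose equal to the Week 4 dose, and Protocol 3.1 allows no GC adjustment during the 4 weeks. The GC change at Week 4 is therefore zero by construction. The GC half of 13.1.1 cannot add a responder in these cohorts; read literally, it can only remove one whose GC dose is missing.

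**The case against.** The strongest reply is that the sentence is loose drafting with no demonstrated consequence.

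- 13.1.1 refers to Table 5 rather than replacing it. Its next sentence uses *or* where failure of both components is evidently meant, so the missing-data sentence may be equally loose.
- The SAP appears to expect a GC dose for everyone. It summarises GC dose by scheduled time point (12.3) and Week 12 GC change by cohort and overall (13.2.4), and it relies on the Week 4 dose as baseline (9.4.17.4). If every subject has a GC dose recorded and an A4 result, nothing is lost.
- The elevated-baseline A4 endpoint (13.1.2) and the biomarker reduction proportions (13.2.3) need no GC data. The study is descriptive, and SAP 10.5 already calls for caution.

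Most of this stands as a limit on size and scope. It does not remove the ambiguity, because neither passage says how to score one observed reduction with the other component missing.

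A reader might go further and infer that the GC form is scheduled at end of treatment only for extension entrants, so that the response rate is in fact biased down and follows the choice to continue. There is some indirect support: the adjustment row has no Day 1 entry, and the SAP has to assume the Day 1 dose, which suggests that the form follows the activity. But the documents restrict the adjustment, not completion of the page, and the row carries an X at end of treatment. The inference is plausible, not established. Nor does it reach the Week 8 summary in Cohorts 1-3, where adjustment applies to all.

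**Conclusion.** The point holds as a defect of specification. Read literally, 13.1.1 scores two of the nine data states as failure when the response is already observed. That conflicts with Table 5 code 1, and code 0 does not resolve the conflict. The direction is certain: any error lowers the composite rate. The size is unknown. It is 20 points per affected subject in a cohort of 5 and 10 points in a cohort of 10, and it is zero if no responder has a missing component.

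A link to extension entry rests on an assumption that the documents do not state, namely that the adjustment form is left blank at end of treatment for subjects who do not continue. The 80% versus 40% contrast in a cohort of 5 is one chosen scenario, not an estimate. It is also too strong to say that the SAP contains two settled rules giving different rates, because Table 5 can be read to agree with either scoring.

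For Cohorts 4-9 the problem arises only because 13.1.1 applies the composite in place of their stated A4 endpoint. The correction should be made before database lock.

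**What to change.** 1. Put the same wording in Table 5 and 13.1.1: *Responder if either observed component shows a reduction from baseline. Non-responder if no observed component shows a reduction, or if both components are missing.*
2. For Cohorts 4-9, state in 13.1.1 that response at Week 4 is scored on A4 alone, with no GC data required.
3. Report how many subjects have only one component observed at end of treatment, split by extension entry, so that a reader can see whether the rule mattered.
4. Do not make the Concomitant Medication eCRF a routine substitute for a missing GC dose. SAP Section 15 says that its frequency field is free text and not easily analysed, and a total daily dose needs the frequency. Comparing a baseline from one form with a Week 12 dose from another could also create GC reductions that did not occur. At most, use it in a sensitivity analysis with a reviewed derivation.

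Items 1 to 3 cost a few sentences in the SAP, a small change to the responder derivation and one count table. Item 4 adds nothing unless the sensitivity analysis is chosen; in that case it needs a record-by-record review of GC entries.

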#### 13.1.1.1 Reporting Results

##### 13.1.1.1.1 Descriptive Statistics

Frequency and proportion (expressed as percentages) of responders will be calculated along with 95% Exact (Clopper-Pearson) CIs and reported for the study and each cohort.

##### 13.1.1.1.2 Graph Presentation

The proportion of responders will be displayed graphically over time with the y-axis representing the proportion meeting the responder definition and the x-axis the visits Week 8 and Week 12.

Bar charts with one bar per cohort will display the proportions of responders at a Week 12. This bar chart may be replicated at the additional time point listed below.

### *13.1.1.3 Supportive Summaries*

#### *13.1.1.3.1 Subgroups*

The proportion of responders of the planned subgroup analyses ([Section 10.7](#)) will be summarized.

#### *13.1.1.3.2 Additional Timepoints*

The proportions of responders at the post-baseline protocol scheduled visits will be summarized (Week 8).

### *13.1.2 Elevated Baseline A4 who Achieve a Reduction in A4 at Week 4*

Population: The analysis population for the secondary efficacy analyses is the EBPD analysis set.

Variable: The analysis variable is the proportion of subjects in the EBPD analysis set who are responders (defined in [Table 5](#)). This proportion is calculated for each cohort as the number of subjects at Week 4 who have a reduction of A4, divided by the total number of subjects in the EBPD analysis who were enrolled in each cohort.

Subjects with missing data at a given visit are assumed to be non-responders at that specific visit. Subjects who do not have a reduction from baseline in A4 are considered non-responders.

## **13.2 Exploratory Efficacy Analysis**

### *13.2.1 Change from Baseline in PD Biomarkers*

The PD analysis set will be used for exploratory efficacy analyses.

Descriptive statistics (11-point) for the exploratory biomarker assessments, change from baseline, percent change from baseline, and geometric mean ratio will be presented by cohort, scheduled time points including Baseline, and by subgroup ([Section 10.7](#)). PD biomarkers include ACTH, 17-OHP, A4, and testosterone.

The back-transformed log scale change from baseline and 95% confidence intervals will be calculated for each post-baseline visit by cohort and overall using a balanced bootstrap method. The bootstrapping will consist of 1,000 replicate samples using a uniform random number generation by the method of Fishman and Moore with a SEED = 42, where the sampling unit is the subject ID which uniquely identifies each enrollment experience for a given subject.

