1.2.2. Study Population

The study is expected to enroll approximately 20 children across Cohorts 1, 2, and 3, specifically 10 participants in the 11- to 17-year-old age group (i.e., 5 participants in Cohort 1 and 2) and 10 in the 2- to 10-year-old age group (i.e., 10 participants in Cohort 3). If the optional Cohort 1a is initiated, Cohorts 1-3 may, however, enroll up to approximately 25 children.

This study will also enroll approximately 5 adults aged ≥ 18 years in Cohort 4 and 5-10 adults in Cohort 5. Therefore, up to approximately 15 adults may be enrolled. Cohorts 6 and 7 will enroll approximately 5 children each in the 11-17- and 2-10-year age groups, respectively. If Cohorts 8 and 9 are initiated, each will also enroll approximately 5-10 children. Therefore, up to 30 children may be enrolled in the BID dosing cohorts ([Table 1](#)).

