The study will last approximately 10 weeks including a 2-week Screening Period, a 4-week Treatment Period and a Safety Follow-up visit 30 days after the last dose of study drug). Participants may continue in an extension period upon completion of the 4-week Treatment Period. If participants enroll in the extension after the 4-week Treatment Period, the Safety Follow-up Visit will occur 30 days after the last dose in the extension. Cohorts 4 and 5 will include adults aged ≥ 18 years (up to approximately 5 participants in Cohort 4 and 10 participants in Cohort 5). The 10 participants that may be evaluated in Cohort 5 is to allow for the possibility of more than one dose tested (i.e., 300mg or 400mg BID – per DMC recommendation). Cohorts 6 and 8 will include children ages 11 to 17 years old (up to approximately 5 participants in each cohort) and Cohorts 7 and 9 will include children ages 2 to 10 years old (up to approximately 5 participants in each cohort). Cohorts 8 and 9 may include approximately 5 additional participants each if more than one dose is tested (i.e., 300mg and 400mg equivalent BID). For example, if 5 children are treated with 300mg BID in Cohort 8, the DMC may review safety data from all 5 after 4 weeks of treatment and make a recommendation regarding enrolling another approximately 5 children at 400mg BID ([Table 1](#), [Figure 2](#)).

SPR001-205

Spruce Biosciences, Inc.

CLINICAL STUDY PROTOCOL

Version 5.0

Cohorts 4 and 6 will begin simultaneously with a dose of 200 mg BID in participants aged ≥ 18 years and 200 mg adult equivalent BID in participants aged 11-17 years (200 mg BID has been previously evaluated in adults in study SPR001-202).

The DMC will convene once 4 weeks of safety data is available for 4 sentinels from Cohorts 4 and 6 combined. After reviewing data from these 4 participants (in addition to all other available safety data), the DMC will make a recommendation regarding initiation of Cohorts 5 and 7.

Cohort 5 will enroll adult participants at 300 or 400mg BID (per DMC recommendation) and will provide safety data in adults to support the administration of higher BID doses (i.e., up to 400mg BID) in children and adolescents. Cohort 7 may begin simultaneously with Cohort 5 and will enroll children aged 2-10 years at a dose of 200mg adult equivalent BID.

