8.3.6. Pharmacodynamic Analyses

The PD Population will be used for all PD analyses.

Change from baseline in PD biomarkers, ACTH, 17-OHP, A4, testosterone, and 11KT will be summarized descriptively using the 8-point summary as well as geometric mean ratios comparing baseline to post baseline, as appropriate. T will be summarized separately for males and females.

Change from baseline in select PD ratios will also be summarized, A4/T (males only) and 11KT/T (males and females, separately). Other ratios may be identified in the statistical analysis plan.

The proportion of participants with a reduction in biomarkers at Weeks 4 (all cohorts) and 12 (Cohorts 1 to 3 only) will be summarized descriptively, including by subgroup, baseline A4 \leq ULN, Baseline A4 $>$ ULN:

- Any reduction
- \geq 50% reduction
- A4 \leq ULN

Change from baseline in GC total daily dose at Week 12 and during the extension period will be summarized descriptively:

- Absolute change (mg)
- Absolute change adjusted for body surface area (mg/m²)
- Percent change (%)
- Proportion of participants with GC reduction
- Proportion of participants with baseline dosing $>$ 3x daily who decrease frequency of administration \leq 3x daily

The proportion of participant with a \geq 1 mg/m² GC reduction or any reduction from baseline in A4 at Week 12 will be summarized descriptively.

Changes in adrenal biomarkers and GC will be summarized in a similar manner for the extension period.

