7.1	To evaluate the safety of tildacerfont in subjects with CAH	AEs and SAEs	14.1
8.	Secondary		
8.1	To determine the efficacy of tildacerfont on reduction of glucocorticoid (GC) use in subjects with classic CAH after 4 weeks or 12 weeks of treatment	

• Proportion of subjects who achieve reduction in glucocorticoid (GC) dosing (beyond 12 weeks for Cohorts 1-3 and beyond 4 weeks for Cohorts 4-9)

• Proportion of subjects who achieve approximately physiologic GC dosing (<math>\leq 11 \text{ g/m}^2/\text{d}</math>)

	13.1.1
8.2	To determine the efficacy of tildacerfont on disease control in subjects with classic CAH	

• Proportion of subjects with elevated A4 at completion of treatment period (Week 12 for Cohorts 1-3 and Week 4 for Cohorts 4-9) who achieve a reduction in A4.

• Proportion of subjects with elevated A4 at completion of treatment period who achieve A4 normalization

	13.1.2
9.	Exploratory		
9.1	To explore changes in pharmacodynamic (PD) biomarkers in pediatric subjects with CAH	Change from baseline in adrenocorticotropic hormone (ACTH), 17-hydroxyprogesterone (17-OHP), A4, testosterone, (at Week 4 for all cohorts and Week 12 for Cohorts 1-3)	13.2.1
9.2	To explore the impact of tildacerfont on skeletal maturation	Change from baseline in predicted adult height	5.3.1.4

**Table 4** Detailed Exploratory Objectives and Endpoints

Objective		Endpoint	Section Number
1. Change from baseline over 12 weeks			
1.1.	To explore changes from baseline in pharmacodynamic (PD) biomarkers in pediatric subjects with CAH over 12 weeks	Log-transformed change from baseline in ACTH	13.2.1
1.2.		Log-transformed change from baseline in 17-OHP	13.2.1
1.3.		Log-transformed change from baseline in A4	13.2.1
1.4.		Log-transformed change from baseline in T, by sex	13.2.1
2. Change from baseline in ratios over 12 weeks			
2.1.	To explore changes in select PD biomarkers ratios in pediatric subjects with CAH over 12 weeks	Change from baseline in A4/T ratio (males only)	13.2.2
3. Proportion of subjects with reduction [1] overall and [2] by subgroup (Baseline A4 ≤ ULN; Baseline A4 > ULN) [3] by subgroup (Male; Female)			

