#### 9.4.13 Geometric Mean Ratio and Percent Change

For PD hormone variables (Section 5.3.2), the geometric mean ratio (GMR) and percent change from baseline will be calculated by cohort and dose level. The GMR is derived from the natural logarithm of the post-baseline value divided by the baseline value [ $\log(\text{post-baseline}/\text{baseline})$ ]. The GMR is the exponential function of the mean of  $\log(\text{post baseline}/\text{baseline})$ . The 95% CI of GMR is the exponential function of the 95% CI of the mean [ $\log(\text{post baseline}/\text{baseline})$ ]. The percent change is derived as  $100 \times (\text{GMR} - 1)$ . The 95% CI of percent change is  $100 \times (95\% \text{ CI of GMR} - 1)$ .

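### SAP 13.2.1 bootstraps 95% CIs for hormone change by cohort without naming the interval type; at about 5 subjects the common types cover about 83-85%, and SAP 9.4.13 defines a CI for the same ratio with no method or link

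*SAP*

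**What the plan says.** SAP 13.2.1 says that the log-scale change, transformed back, and its 95% confidence intervals "will be calculated for each post-baseline visit by cohort and overall using a balanced bootstrap method". It then specifies 1,000 replicates, a named random number generator, a seed, and resampling "where the sampling unit is the subject ID which uniquely identifies each enrollment experience for a given subject". Nothing says whether the limits are percentile, basic, BCa, normal or studentized.

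SAP 9.4.13 covers the same quantity. It defines the geometric mean ratio (GMR) as the exponential of the mean log ratio of post-baseline to baseline. It says of the interval: "The 95% CI of GMR is the exponential function of the 95% CI of the mean" log ratio. How the CI of that mean is formed is not stated. The layout is that the GMR and "percent change from baseline will be calculated by cohort and dose level", whereas 13.2.1 refers to cohort and overall. SAP 9.1 also lists a GMR with a 95% CI in the 11-point summary, again without a method. None of the three sections refers to another on this point.

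On size, Protocol 1.2.2 states that "Cohorts 6 and 7 will enroll approximately 5 children each". Protocol Table 1 plans 5 for Cohorts 1, 1a, 2 and 4 and about 10 for Cohort 3. Cohort 5 plans 5 per dose, and Protocol 3.1 adds that "Cohorts 8 and 9 may include approximately 5 additional participants each if more than one dose is tested".

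**The concern.** With very few subjects the type of bootstrap interval matters. For a mean of 5 values the percentile, basic, BCa and normal types are too narrow for two reasons. The resampling distribution uses the variance with divisor n rather than n-1, and no allowance is made for estimating the SD from 4 degrees of freedom. Back-transformation does not repair this, because exponentiation is monotone and leaves coverage unchanged.

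Two programmers using the same seed could therefore report different 95% limits, and the common choices would be well below 95% in most cohorts. If 9.4.13 is programmed as a t interval and 13.2.1 as a percentile interval, the report would show two 95% CIs for one estimate, the second about 0.62 times as wide as the first on the log scale.

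Elsewhere the SAP is specific: 13.1.1.1.1 names Clopper-Pearson limits for the responder proportions. SAP 3.1 commits to reproducible analysis, and SAP 4 says that the planned analyses may go into submissions and manuscripts.

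**Working it through.** The documents give no coverage or precision figure for this analysis, only the nominal 95%, so there is no planned figure to reproduce.

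**Inputs.** From the SAP: 95% level, balanced bootstrap, 1,000 replicates. From the protocol: n about 5 for most cohorts and for each dose in Cohorts 5, 8 and 9; n about 10 for Cohort 3. Assumptions: the statistic is the mean log ratio, and log changes are normal, with an exponential shape as a check on skew.

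**Closed form for the normal type.** The bootstrap SE of the mean is s*sqrt((n-1)/n)/sqrt(n). Limits at 1.96 such SEs therefore cover P(|t(n-1)| < 1.96*sqrt((n-1)/n)).
- n=5: 1.96*sqrt(4/5) = 1.753, and P(|t(4)| < 1.753) = 84.6%. Width relative to t: 1.753/2.776 = 0.63.
- n=4: 81.2%. n=10: 90.4%. n=20: 92.9%.

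**Simulation of the SAP's scheme.** 20,000 simulated cohorts at n=5 and 5,000 at the other sizes, normal log changes. Coverage (%):

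| n | percentile | basic | BCa | normal | studentized | t | percentile width / t width |
|---|---|---|---|---|---|---|---|
| 4 | 80.2 | 80.5 | 80.0 | 81.5 | 94.8 | 95.6 | 0.52 |
| 5 | 83.3 | 83.3 | 83.3 | 84.3 | 94.5 | 95.0 | 0.62 |
| 10 | 90.1 | 90.4 | 89.9 | 90.5 | 95.1 | 95.1 | 0.81 |
| 20 | 92.9 | 92.9 | 92.7 | 93.3 | 95.0 | 95.0 | 0.91 |

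The Monte Carlo SE is about 0.3 points at n=5 (sqrt(0.833*0.167/20000)) and about 0.4 points at n=10 (sqrt(0.9*0.1/5000)). Separate runs gave 89.4% and 91.0% for percentile at n=10, a wider spread than sampling error readily explains, so that figure is best read as about 90%. At n=5 all runs agree within 0.4 points for percentile.

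**Consequence at n=5.** With no true change, the four common types exclude no change in about 100 - 84.6 = 15.4% to 100 - 83.3 = 16.7% of cohorts, instead of 5%.

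**Skew check, exponential log changes, n=5 (8,000 cohorts).** Percentile 78.0%, basic 75.7%, BCa 79.2%, normal 77.9%, t 88.0%, studentized 92.5%.

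**Width in hormone units.** The SD of log change is not in the documents, so 0.4, 0.6 and 0.8 are assumed. The t half-width at n=5 is 2.776*SD/sqrt(5) = 0.497, 0.745 and 0.993; multiplying by 0.62 gives the percentile half-width. After exponentiation the t interval runs from the ratio divided by to the ratio multiplied by 1.64, 2.11 or 2.70. The percentile interval uses 1.36, 1.59 or 1.85.

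**The case against.** The strongest reply is that the SAP never chooses a poor interval. It chooses none, and a studentized bootstrap would be close to nominal. SAP 9 also sends presentation conventions to a separate mock-shell document, which might name the type. And 9.4.13 can be read as an ordinary t interval, in which case a sound CI is already planned. This stands in part. A reader might infer that the planned intervals do under-cover, or that 9.4.13 contradicts 13.2.1. The documents support neither. They show an unnamed type, for which four common choices perform badly, and two sections whose relation is unstated. A plan that fixes the seed should also fix the limits.

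Second, cohort sizes may not be 5. Protocol 1.2.3 reports 30 children in Cohorts 1-3 against 20 to 25 planned, an average of 10 over three cohorts or 7.5 over four. Against that, SAP 13 excludes efficacy data collected under Protocol v3.0, and missed samples also lower n. The size is therefore uncertain in both directions. The shortfall is about 5 points at n=10 and about 2 at n=20, so pooled intervals are much less affected.

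Third, the practical weight is limited, and this stands. The summaries are exploratory, SAP 10.5 promises cautious interpretation, Protocol 8.3.6 asks for no CI, and no decision rule uses these limits.

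**Conclusion.** The point holds as a specification gap with a measurable effect at the planned cohort size. Under normality and n=5, percentile, basic, BCa and normal limits cover about 83-85%, against about 95% for t and 94-95% for studentized. Skew lowers the coverage of all of them. The figures rest on a mean log ratio as the statistic and on about 5 evaluable subjects per cohort.

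Two further inferences should not be drawn.
- **Testosterone by sex.** SAP Table 4 lists "Log-transformed change from baseline in T, by sex" and Protocol 8.3.6 says "T will be summarized separately for males and females". In a cohort of 5 the smaller sex group has at most 2 subjects. At n=2 each resample made of one value repeated has probability 1/4, above 2.5%, so a percentile interval would simply be the two observed values and would cover 50% for symmetric data. But the bootstrap sentence says only by cohort and overall, and the subgroup wording belongs to the descriptive summary. A bootstrap by sex within cohort is not clearly planned.
- **Re-enrolment.** Because the resampling unit is the enrolment, a reader might conclude that an overall interval is materially too narrow. SAP 13.2.1 does not define overall, and the available text gives neither the number of repeat enrolments nor a within-person correlation. The effect cannot be sized and forms no part of this finding.

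**What to change.** In SAP 13.2.1 and 9.4.13, specify one by-cohort interval: the t interval with n-1 degrees of freedom on the mean of log(post/baseline), exponentiated. State that it is the interval meant in both sections and in the 11-point summary, and say how cohorts with two doses are handled, since only 9.4.13 mentions dose level.

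If a bootstrap is kept, name the studentized type and say which interval is reported. Also say how resamples with zero variance are treated: at n=5 they occur with probability 5*(1/5)^5 = 0.16%, and at n=4 with probability 4*(1/4)^4 = 1.6%.

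If any summary is split within cohort, for example testosterone by sex, show individual ratios without a CI for groups of 1 or 2.

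The cost is SAP wording, and less programming than the bootstrap. The downside is that cohort intervals become about 1/0.62 = 1.6 times wider on the log scale at n=5 than percentile limits. The t interval still under-covers with strong skew (about 88% with exponential log changes at n=5). The studentized bootstrap does better there (about 93%) but is wider again: even with normal data its median width is about 1.3 times the t interval at n=5 and 1.9 times at n=4.
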